- ORR, DOR, and PFS based on HPV status and PD-L1 expressions (combined positive score [CPS] ≥ 1 and CPS ≥ 20)

Exploratory Endpoints:

- Response in injected and noninjected target lesions per intratumoral Response Evaluation Criteria in Solid Tumors (itRECIST) by Investigator assessment
- Baseline, and change from Baseline, in tumor or blood measurements of biomarkers related to TLR9, immune checkpoints, and potential markers of resistance or response to immunotherapy
- Change from Baseline in blood concentrations of C-X-C motif chemokine 10 (CXCL10) (IP-10) and other cytokines after treatment with CMP-001
- Blood concentrations of CMP-001 or its metabolites

Methodology:

This is a multicenter, open-label, Phase 2 clinical trial of CMP-001 administered by IT injection in combination with intravenous (IV) pembrolizumab in subjects with recurrent or metastatic head and neck squamous cell carcinoma (HNSCC) not previously treated with a PD-1 blocking antibody. This will be a Phase 2 study, with response and DOR assessments using RECIST v1.1 and iRECIST criteria according to Investigator assessment. All subjects will receive CMP-001 IT and pembrolizumab IV according to the treatment schedule until a reason for treatment discontinuation is reached.

Number of subjects (planned):

A total of 43 subjects is planned for this study. This is based on the following assumptions:

- A historical ORR of 19% with pembrolizumab monotherapy in subjects with HNSCC who have a CPS ≥ 1 and were not previously treated with a PD-1 blocking antibody (null hypothesis)
- An anticipated ORR of 35% with CMP-001 and pembrolizumab (alternative hypothesis).
- Power of 80% and one-sided alpha level of 0.05.

Diagnosis and main criteria for inclusion:**Inclusion criteria:**

Subjects enrolled in the study must meet all of the following inclusion criteria to be eligible:

1. Subjects with histologically- or cytologically-confirmed recurrent or metastatic HNSCC considered incurable by local therapies, and subjects with T4 or N3 disease who are ineligible for or refusing local therapies.
2. No prior systemic therapy in the recurrent or metastatic setting. Systemic therapy as part of multi-modal treatment for locally advanced disease is allowed.
3. Primary tumor locations of oropharynx, oral cavity, hypopharynx, larynx, paranasal sinus, or HNSCC of unknown primary origin. Participants may not have a primary tumor site of nasopharynx (any histology).

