- b. The 30-Day Follow-up is a safety follow-up visit that may be conducted in the study clinic OR via phone. This visit should occur 30 days (+7) after the EOT visit.
- c. PTFU will be conducted every 3 months (\pm 2 weeks) for all subjects who discontinue study treatment but have not met criteria for study discontinuation. These subjects should remain on study and receive disease assessments every 3 months, until discontinuation.
- d. LTSFU will be conducted every 3 months (\pm 4 weeks) after the EOT visit or the last disease assessment date in PTFU and may occur by phone call.
- e. CMP-001 Injection Visits: Weekly Dosing (W1D1 and W2D1): The first dose of CMP-001 may be administered SC or IT, at the discretion of the Investigator; all subsequent doses are planned to be administered IT until no injectable lesions remain. A window of $-2/+5$ days is permitted for CMP-001 dosing on W2D1. Q3W Dosing (W4D1+): A window of ± 3 days is permitted for CMP-001 dosing from W4D1 throughout the trial. When pembrolizumab is permanently discontinued, CMP-001 must also be permanently discontinued. Refer to Section 5.4 for Treatment Compliance.
- f. Pembrolizumab dosing will begin on W1D1 and continue Q3W throughout the study. When CMP-001 injection and pembrolizumab dosing fall on the same day, the CMP-001 injection will be given before pembrolizumab dosing. Refer to Section 5.1.1 for Pembrolizumab Dosing.
- g. A full PE will be conducted at Screening and EOT. If the Screening full PE is performed > 72 hours before the W1D1 visit, then a brief (symptom directed) PE must be performed within 72 hours before the first injection of CMP-001. Brief PEs focused on areas of disease or AEs must be performed at every CMP-001 injection visit, and at any other time as clinically indicated. Height will be obtained at Screening only and weight at all PE assessments.

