4.5. Treatment Discontinuation

Study treatment should continue until 1 of the following occurs:

- Unacceptable adverse event that precludes further study treatment (see Section 5.1.2.5.4 and Section 5.1.3)
- 2 years of study treatment
- PD per RECIST v1.1; continuation of treatment through suspected pseudo-progression is permitted at the Investigator's discretion until confirmed PD per iRECIST (Section 7.2.5)
- Upon request of the Sponsor or regulatory agency
- Clinical disease progression

- If medically necessary in the opinion of the Investigator
- Subject withdraws consent for treatment (note that a subject who withdraws consent for additional study treatment and procedures but not for antitumor response will continue to be followed)
- Subject becomes pregnant or begins breastfeeding
- Subject is lost to follow-up
- Death
- End of Clinical Trial

Subjects who permanently discontinue treatment with pembrolizumab because of immune-mediated AEs must also permanently discontinue treatment with CMP-001.

Subjects will continue study treatment until they reach a reason for treatment or study discontinuation. Clinically stable subjects may continue study treatment beyond RECIST v1.1 progression based upon Investigator judgement of potential benefit. Study treatment may not continue beyond 2 years from initial dose of study treatment.

If a subject achieves and maintains a confirmed CR or iCR by Investigator review, treatment with CMP-001 or the combination of CMP-001 and pembrolizumab may be discontinued at the Investigator's discretion once they meet both of the following criteria:

- Subject has been treated with both study drugs for at least 24 weeks
- Subject has received at least 3 doses of both study drugs beyond the date of the initial CR/iCR

NOTE: 3 doses are required only if medically feasible in the Investigator's opinion – less than 3 doses are acceptable if the Investigator is not medically able to inject.

Subjects who discontinue study treatment should undergo the EOT assessments per [Table 1](#). Subjects who discontinue study treatment for reasons other than disease progression (per RECIST v1.1 or iRECIST by Investigator, or clinical PD per Investigator) should remain on study for PTFU (Section [7.6](#)) and LTSFU (Section [7.7](#)) and receive disease assessments according to the Schedule of Assessments ([Table 1](#)).

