As of the data cutoff date, the number and percentage of subjects who screen fail and enroll in the study (receive at least one dose of study treatment), discontinue study treatment, and discontinue the study will be summarized for all screened subjects. The primary reason for treatment(s) and study discontinuation will also be summarized for Treated Analysis Set. Additionally, subgroup analysis of disposition by schedule will also be performed. Subject disposition will be presented in a by-subject data listing.

Study treatment (CMP-001 only or both CMP-001 and Pembrolizumab) may be discontinued for any of the following occurrences:

- Adverse Event
- PD per RECIST v1.1
- Subject Achieved and Maintained a Confirmed CR or iCR (and has been treated for at least 24 weeks, and has received at least 2 doses of both study treatments beyond the date of initial CR/iCR)
- Upon Request of the Sponsor or Regulatory Agency

Regeneron Pharmaceuticals Inc. / Protocol: CMP-001-007
IQVIA Biotech (Confidential) Project # SZA56629

- Clinical Disease Progression
- Medically Necessary in the Opinion of the Investigator
- Subject Withdrew Consent for Treatment
- Subject Became Pregnant or Began Breastfeeding
- Subject Lost to Follow-up
- Death
- Subject Completed 2 Years of Study Treatment
- End of Clinical Trial
- Other

Study Participation may be discontinued for any of the following occurrences:

- Completed
- Adverse Event
- Subject Withdrew Consent
- Lost to Follow-Up
- Death
- Study Terminated by Sponsor
- End of Clinical Trial
- Other

Percentages of subjects who withdrew for each of these reasons will be calculated using all members of the relevant analysis set for the denominator.

C. Protocol Deviations and Population Inclusions

All protocol deviations will be captured electronically outside of the Electronic Data Capture (EDC) system in the IQVIA Biotech IL-2 system and presented in a by-subject data listing. All deviations will be reviewed on an ongoing basis and classified as major or minor following study review process.

VIII. Efficacy Analyses

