No PD per RECIST v1.1 or Death as of data cutoff date and subject not received new anticancer therapy or received it after the data cutoff date	Censored	Date of last disease assessment on/before data cutoff date	Alive without Documented PD
No PD per RECIST v1.1 or Death as of data cutoff date and new anticancer therapy started before the data cutoff date	Censored	Date of last disease assessment prior to new anticancer therapy	Subsequent Anti-cancer Therapy without Documented PD
PD per RECIST v1.1 or Death after new anticancer therapy and the new anticancer started before data cutoff date	Censored	Date of last disease assessment prior to new anticancer therapy	Documented PD or Death after Subsequent Anti-cancer Therapy
PD per RECIST v1.1 or Death after new anticancer therapy and the new anticancer started after data cutoff date	Censored	Date of last disease assessment on/before data cutoff date	Documented PD or Death after Subsequent Anti-cancer Therapy
PD per RECIST v1.1 or Death immediately following two or more consecutive disease assessments missed since the last adequate disease assessment	Censored	Date of last adequate tumor assessment prior to missing assessments	PD or Death after Missing ≥ 2 Consecutive Disease Assessments
Withdrew consent or lost to follow-up before PD per RECIST v1.1 or Death	Censored	Date of last adequate disease assessment	Discontinued from Study without Documented PD or Death

Table 1b: Censoring Rules for the iPFS/iDOR

Situation	Outcome	Date	Event Description/ Censoring Reason
iCPD per iRECIST between scheduled disease assessments on/before new anticancer therapy or data cutoff date,	Event	Earliest date of tumor assessment documenting iUPD	iCPD per iRECIST

Regeneron Pharmaceuticals Inc. / Protocol: CMP-001-007
 IQVIA Biotech (Confidential) Project # SZA56629

whichever is earlier			
Death without iCPD per iRECIST and not receiving new anticancer therapy on/before data cutoff date	Event	Date of death	Death without iCPD per iRECIST
iPFS only iUPD per iRECIST at the time of PD per RECIST v1.1, continued study treatment without further tumor assessments as of data cutoff date	Censored	Date of the last tumor assessment on/before data cutoff date	No Adequate Disease Assessment per iRECIST

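### Clinical progression stops treatment but is not a PFS event; where RECIST progression is not captured the subject is censored, which biases PFS upward, and no sensitivity analysis is planned

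*Protocol*

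**What the plan says.** PFS runs from first dose to RECIST v1.1 progression or death (SAP IV.B and VIII.A). Clinical progression is a separate reason for stopping treatment, listed apart from RECIST progression (Protocol 4.5; SAP VII.B, "Clinical Disease Progression"). SAP Table 1a has no row for it. The rows that can apply to such a subject are:

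- Alive, no RECIST progression, no new therapy: censored at the last assessment.
- "No PD per RECIST v1.1 or Death as of data cutoff date and new anticancer therapy started before the data cutoff date": censored at the last assessment before that therapy. Progression or death after the therapy is censored at the same point.
- "PD or Death after Missing ≥ 2 Consecutive Disease Assessments": censored at the last adequate assessment before the gap.
- No post-baseline assessment: censored at first dose.
- Death without RECIST progression and without new therapy: an event.

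For response, SAP VIII.A gives a subject who stops for disease progression before any post-baseline assessment a best response of PD.

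On imaging after treatment, Protocol 4.5 assigns follow-up scans to "Subjects who discontinue study treatment for reasons other than disease progression (per RECIST v1.1 or iRECIST by Investigator, or clinical PD per Investigator". Table 1 footnote c covers everyone off treatment who has not met the study-discontinuation criteria: "These subjects should remain on study and receive disease assessments every 3 months, until discontinuation". Section 4.6 does not list clinical progression among those criteria. Section 7.6 ends scanning at disease progression without saying whether clinical progression counts. Table 1 also schedules imaging at the end-of-treatment (EOT) visit, and footnote a places that visit within 7 days of stopping.

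SAP VIII.C plans Kaplan-Meier medians and landmark rates for PFS, with no sensitivity analysis.

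**The concern.** Kaplan-Meier estimation assumes that a censored subject has the same future risk as those still followed. A subject stopped for clinical progression has been judged by the investigator to be failing. If RECIST progression is never recorded, Table 1a removes that subject from the risk set as though nothing had happened, and in two situations a later death does not count either. Landmark PFS is then too high.

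Site practice can add to this, because the protocol supports two readings of who is scanned after treatment. The SAP also does not say whether assessments that Section 4.5 no longer schedules count as missed, and that decides whether a later death is an event or is censored.

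The two endpoints also treat the same early failure differently. A subject who stops for progression before the first scan is PD for response but contributes nothing to PFS.

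**Working it through.** **The plan's own figure.** The documents state no PFS assumption. The only design figure is the planned sample size of 43, set on response: "A historical ORR of 19% with pembrolizumab monotherapy in subjects with HNSCC", "An anticipated ORR of 35% with CMP-001 and pembrolizumab", "Power of 80% and one-sided alpha level of 0.05".

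n = [(1.645·√(0.19·0.81) + 0.842·√(0.35·0.65)) / 0.16]² = 42.8, rounded up to 43, with power 80.1% at 43. It reproduces, and nothing below changes it.

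**Inputs for PFS.** From the documents: scans at Week 10 Day 1 and every 9 weeks after (9 weeks = 63/30.4375 = 2.07 months), the Table 1a rules, and 24 subjects (SAP II.C). Assumed: exponential PFS with a true median of 3 or 5 months, and a share f of 10, 20 or 30% of progressions declared clinically first (0.1, 0.2, 0.3 × 24 = about 2, 5 or 7 subjects). Also assumed are the proportion of these whose EOT scan shows RECIST progression and the proportion of the rest who die as a countable event.

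**Hand check, worst case (no EOT detection, no countable deaths), true median 3 months.** Let S(t) = 2^(−t/3) and a = S(2.07) = 0.620. Two scans fall before 6 months; the third is at 6.21.

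- Clinical progression counted as an event: (1−f)·S(4.14) + f·S(6). With f = 0.3: 0.7·0.384 + 0.3·0.250 = 0.344.
- SAP rules: in each scan interval the clinical progressors leave the risk set before the next scan, so each Kaplan-Meier factor is a/(1−f(1−a)). With f = 0.3: 0.620/(1−0.3·0.380) = 0.700, and 0.700² = 0.49.

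The simulation gives 0.344 and 0.489. The formula also shows that it matters little here whether the censoring date is the previous 9-weekly scan or a negative EOT scan shortly after stopping. Either way the subject is normally gone before the next scan at which events are recorded.

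**Simulation (400,000 subjects per scenario, 24-month cutoff).** Each cell is 6-month PFS in %, with clinical progression as an event → under Table 1a, and the shift in points.

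| True median; EOT detection; countable deaths in the rest | f = 10% | f = 20% | f = 30% |
|---|---|---|---|
| 3 mo; 0%; 0% (worst) | 37.0→41.5 (4.5) | 35.7→45.0 (9.3) | 34.4→48.9 (14.5) |
| 3 mo; 50%; 40% | 37.1→38.9 (1.8) | 35.6→39.2 (3.6) | 34.5→39.8 (5.3) |
| 3 mo; 80%; 40% | 37.1→37.8 (0.8) | 35.7→37.3 (1.6) | 34.3→36.6 (2.3) |
| 5 mo; 0%; 0% (worst) | 55.0→59.2 (4.2) | 53.7→62.3 (8.7) | 52.6→65.9 (13.3) |
| 5 mo; 50%; 40% | 54.9→56.6 (1.7) | 53.7→57.0 (3.3) | 52.6→57.6 (5.0) |
| 5 mo; 80%; 40% | 54.9→55.7 (0.8) | 53.8→55.3 (1.5) | 52.5→54.7 (2.2) |

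(Shifts were computed before rounding.) The as-event figure falls as f rises because clinical progression is dated when it occurs, while RECIST progression waits for the next scan.

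In 4,000 trials of 24 subjects (true median 3 months, worst case) the mean 6-month PFS was 37.3→41.8, 35.6→44.9 and 34.3→48.9, so the small sample does not alter the pattern.

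**Median.** It moved in 2 of the 30 scenarios run (2 medians × 3 shares × 5 combinations of detection and deaths), both at f = 30% with a 5-month true median and no EOT detection: 6.2 to 8.3 months with no countable deaths, and 6.2 to 7.0 with 40%. The larger change is one step on the scan grid, from 27 to 36 weeks.

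**The case against.** The strongest case on the other side is that the protocol already limits the problem. Section 4.5 itself sends everyone who stops treatment to the EOT assessments, which include imaging. Appendix D asks sites to try hard to document objective progression after treatment stops. A death without new therapy, and not after two missed assessments, is an event. Section 3.1, SAP II.A and Table 1 footnote c keep in follow-up anyone who has not left the study. Reasons for stopping and for censoring are to be tabulated, and data are listed by subject. PFS is secondary, SAP II.C makes all analyses descriptive and exploratory, and at 24 subjects the sampling SD of a 6-month rate near 50% is about √(0.5·0.5/24) = 10 points.

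Much of this stands. A reader of Section 4.5 alone might infer that clinical progressors all leave scanning and are all censored at their last scan. The documents do not support that, because of the EOT scan, the countable deaths and the wording of footnote c. A reader might also infer that PFS will be set against external data. No such comparison is planned: the only historical benchmark is for ORR, and the Introduction's summary of the pembrolizumab monotherapy trial gives no PFS.

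The safeguards are nevertheless incomplete. An EOT scan may fall short of the RECIST threshold in a subject who is clinically failing. The 7-day EOT window can also collide with Section 7.2.4, which discourages imaging an injected lesion within 2 weeks of injection unless medically necessary. The censoring reasons in Table 1a have no category for clinical progression, so the planned tabulation would not separate these subjects from others who are alive without progression. Sampling error does not excuse a shift that was in one direction in every scenario.

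**Conclusion.** The point holds in this form: clinical progression is not a PFS event, Table 1a does not address it, the passages on post-treatment scanning conflict, the resulting censoring is informative, its direction is upward, and no sensitivity analysis is planned.

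The size cannot be fixed from the documents, which give no rate of clinical progression and no yield for the EOT scan. For assumed shares of 10–30%, 6-month PFS is raised by about 1–2 points if the EOT scan catches most cases, about 2–5 in the intermediate case and about 4–15 at worst. The worst-case figures should not be read as the expected bias, and a large inflation of median PFS is not supported. The primary ORR is unaffected. This is a worthwhile, inexpensive improvement to a secondary descriptive estimate and no threat to the study's main result.

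**What to change.** 1. Keep RECIST v1.1 PFS as the main analysis.
2. Add one sensitivity PFS to SAP VIII.C. Treatment discontinuation recorded as "Clinical Disease Progression" without earlier RECIST progression is an event on the recorded date, including in subjects with no post-baseline scan. Later deaths in these subjects then need no separate rule, and early failures are treated consistently with the best-response rule in SAP VIII.A.
3. Reconcile Protocol 4.5, 4.6, 7.6 and Table 1 footnote c on who stays in post-treatment scanning, and state in the SAP whether assessments that were not scheduled count as missed.

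The cost is one extra Kaplan-Meier table from a discontinuation reason and an end-of-treatment date that are already collected. The drawback is that clinical progression is more subjective than RECIST progression, particularly in an open-label study, so this should remain a sensitivity analysis.

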4.6. Study Withdrawal

Subjects may withdraw from the study at any time and without penalty or loss of future medical care, or any other benefits to which they are otherwise entitled. Subjects will be withdrawn from the study for any of the following reasons:

- Subject withdraws consent for the study
- Subject lost to follow-up
- Death
- End of clinical trial

For subjects who withdraw consent from overall study participation (not only study treatment) will not have the EOT visit, safety follow-up visits, or further evaluations performed.

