7.7. Long-Term Survival Follow-Up

Subjects who discontinue study treatment and PTFU, will be contacted by the site according to the Schedule of Assessments ([Table 1](#)) for LTSFU, which will continue until death, withdrawal of consent, lost to follow-up, or End of Clinical Trial.

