All events of RECIST v1.1 disease progression or death will be counted regardless of whether the event occurred while the subject was on study drug or had previously discontinued treatment. Subjects who do not experience disease progression or death before the analysis cutoff date will be censored at the date of last adequate tumor assessment. Date of censoring for these subjects will be based on the last tumor assessment prior to missing the assessments. For subjects who started a subsequent anti-cancer therapy before having a documented PD, the overall response assessment evaluated after new anti-cancer treatment will not be considered for PFS calculation, and the last disease assessment prior to the start of the subsequent therapy will be used. Censoring rules are summarized in Table 1a. If a subject meets the criteria for more than one censoring rule, PFS will be censored at the earliest censoring date.

Overall Survival (OS). Overall survival will be calculated as the time from first dose of study treatment to the date of death due to any cause. Subjects who are alive at the time of analyses will be censored at the time of last known alive date, or at data cutoff date, whichever occurs first. Censoring rules are detailed in Table 1c. The last contact date will be derived as [Table 2](#).

Regeneron Pharmaceuticals Inc. / Protocol: CMP-001-007
IQVIA Biotech (Confidential) Project # SZA56629

OS will be calculated as follows:

$$\text{OS (months)} = (\text{Death or Censoring Date} - \text{First Dose Date} + 1) / 30.4375$$

Immune Objective Response Rate (iORR). iORR is defined as the proportion of subjects with a best overall immune response (iBOR) of confirmed immune complete response (iCR) or confirmed immune partial response (iPR) based on immunotherapy Response Evaluation Criteria in Solid Tumors (iRECIST) by Investigator assessment.

Subjects who continue study treatment beyond PD per RECIST v1.1 will be assessed by the Investigator according to iRECIST. Subjects with an iCR or iPR per iRECIST must have a confirmatory assessment performed at least 4 weeks after the initial assessment where response was declared by the Investigator and all scans should be performed at least 2 weeks after the previous CMP-001 IT injection to prevent injection-related pseudo-progression.

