iUPD per iRECIST, continued study treatment with subsequent disease assessments but no confirmed PD (i.e., iCPD not assigned) or Death as of data cutoff date and subject not received new anticancer therapy or received it after the data cutoff date	Censored	Date of the last tumor assessment as of data cutoff date	Alive without Documented iCPD
iUPD per iRECIST, continued study treatment, but started a new anti-cancer therapy before data cutoff date without evidence of iCPD or Death	Censored	Date of the last tumor assessment prior to new anti-cancer therapy	Subsequent Anti-cancer Therapy without Documented iCPD
iCPD per iRECIST or Death after new anticancer therapy and the new anticancer started before data cutoff date	Censored	Date of last disease assessment prior to new anticancer therapy	iCPD or Death after Subsequent Anti-cancer Therapy
iCPD per iRECIST or Death after new anticancer therapy and the new anticancer started after data cutoff date	Censored	Date of last disease assessment on/before data cutoff date	iCPD or Death after Subsequent Anti-cancer Therapy
iUPD per iRECIST, continued study treatment, iCPD or Death immediately following two or more consecutive disease assessments since the last adequate disease assessment	Censored	Date of last adequate tumor assessment prior to the first missed assessment	iCPD or Death after Missing ≥ 2 Consecutive Disease Assessments
Withdraw consent or lost to follow-up before iCPD per iRECIST or death	Censored	Date of last adequate disease assessment	Discontinued from Study without Documented iCPD or Death

Table 1c: Censoring Rules for the OS

Situation	Outcome	Date	Event Description/ Censoring Reason
Death on/before data cutoff date	Event	Date of death	Death
Alive with study completed before data cutoff date	Censored	Study completion date	Alive on or before study completion date
Alive or death after data cutoff date with study continuing on/till after data cutoff date	Censored	Data cutoff date	Alive on or before data cutoff date

Regeneron Pharmaceuticals Inc. / Protocol: CMP-001-007
 IQVIA Biotech (Confidential) Project # SZA56629

Lost to follow-up prior to data cutoff date	Censored	Last known alive date	Discontinued from study
Discontinued study without death and not lost to follow-up on/prior to data cutoff date	Censored	Date of study discontinuation	Discontinued from study

Table 2: Last Contact Date for the Overall Survival

Source Data	Conditions

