- Subjects with pembrolizumab-related TEAEs
- Subjects with grade 3 or higher TEAEs Related to CMP-001 and/or Pembrolizumab
- Subjects with grade 3 or higher CMP-001-related TEAEs
- Subjects with grade 3 or higher pembrolizumab-related TEAEs
- Subjects with treatment-emergent Serious AEs (SAEs)
- Subjects with SAE Related to CMP-001 and/or Pembrolizumab
- Subjects with CMP-001-related SAEs
- Subjects with pembrolizumab-related SAEs
- Subjects with AE of Special Interest

Regeneron Pharmaceuticals Inc. / Protocol: CMP-001-007
IQVIA Biotech (Confidential) Project # SZA56629

- Subjects with TEAEs leading to CMP-001 and/or Pembrolizumab Treatment Discontinuation
- Subjects with TEAEs leading to CMP-001 treatment discontinuation
- Subjects with TEAEs leading to Pembrolizumab Treatment Discontinuation
- Subjects with TEAEs leading to study discontinuation
- Subjects with TEAEs resulting in death

In addition, the following TEAE summaries tables will be generated. Percentages will be based upon the number of subjects in the Treated Analysis Set.

- All TEAEs, by MedDRA SOC and preferred term
- Grade 3 or higher TEAEs, by MedDRA SOC and preferred term
- TEAEs by maximum severity, by MedDRA SOC and preferred term
- TEAEs Related CMP-001 and/or pembrolizumab by maximum severity, by MedDRA SOC and preferred term
- TEAEs Related CMP-001 by maximum severity, by MedDRA SOC and preferred term
- TEAEs Related Pembrolizumab by maximum severity, by MedDRA SOC and preferred term TEAEs by highest relationship to CMP-001 and/or Pembrolizumab, by MedDRA SOC and preferred term
- Grade 3 or higher TEAEs Related to CMP-001 and/or pembrolizumab by MedDRA SOC and preferred term
- Grade 3 or higher CMP-001-related TEAEs, by MedDRA SOC and preferred term
- Grade 3 or higher pembrolizumab-related TEAEs, by MedDRA SOC and preferred term
- Death due to TEAEs, by MedDRA SOC and preferred term
- Serious AEs (SAEs), by MedDRA SOC and preferred term
- Grade 3 or higher SAEs, by MedDRA SOC and preferred term
- Grade 3 or higher CMP-001-related SAEs, by MedDRA SOC and preferred term
- Grade 3 or higher pembrolizumab-related SAEs, by MedDRA SOC and preferred term
- SAEs related to treatment (possibly + probably + definitely), by MedDRA SOC and preferred term
- SAEs related to CMP-001 by MedDRA SOC and preferred term
- SAEs related to pembrolizumab by MedDRA SOC and preferred term
- TEAEs leading to CMP-001 and/or Pembrolizumab treatment discontinuation

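### SAP VII.B allows study exit for Adverse Event or Other and Table 1c censors OS at that exit, while the Protocol keeps such subjects in survival follow-up; OS may be informatively censored if vital status is not sought afterwards

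*Protocol*

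**What the plan says.** **Protocol.** Section 4.6 opens its list with "Subjects will be withdrawn from the study for any of the following reasons" and names four: consent withdrawn, lost to follow-up, death, end of trial. An unacceptable adverse event appears in section 4.5, as a reason to stop treatment. Section 4.5 also says what follows: "Subjects who discontinue study treatment for reasons other than disease progression" stay on study for posttreatment and long-term survival follow-up (LTSFU). Section 7.7 provides "for LTSFU, which will continue until death, withdrawal of consent, lost to follow-up, or End of Clinical Trial". Table 1 schedules those contacts every 3 months, and they may be made by phone.

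**SAP.** Section VII.B (Disposition) says "Study Participation may be discontinued for any of the following occurrences" and lists eight categories, among them Adverse Event and Other. Section IX.B plans a summary row "Subjects with TEAEs leading to study discontinuation", separate from the rows for stopping CMP-001 or pembrolizumab. For OS, Table 1c has a row "Discontinued study without death and not lost to follow-up on/prior to data cutoff date", which censors at the date of study discontinuation under the label Discontinued from study. The OS text in section VIII.A gives a different date: "Subjects who are alive at the time of analyses will be censored at the time of last known alive date, or at data cutoff date", taking the earlier of the two.

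**The concern.** The Kaplan-Meier method treats a censored subject as having the same later risk of death as those still followed. That is doubtful for someone taken off study because of toxicity. Under the Protocol such a subject is still contacted quarterly and a later death is observed. Read literally, the SAP categories and the Table 1c row let follow-up for OS stop at the exit.

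At stake is the OS curve, a secondary endpoint in 24 treated subjects, where one or two lost deaths are visible. The planned display of censoring reasons would not show the problem. Table 1c gives the same label to subjects lost to follow-up and to subjects who left for any other reason, so an adverse-event exit cannot be told apart there. No OS sensitivity analysis is planned.

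**Working it through.** The plan gives no figure for this point. Its one design calculation, 43 subjects for response rate, plays no part here. The check is a comparison of rules, then an illustration of size.

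**Step 1: who may leave follow-up.**
- Protocol 4.6 and 7.7: the same four reasons end study participation and survival follow-up.
- Protocol 4.5: stopping treatment for an adverse event does not end follow-up.
- SAP VII.B: eight categories. Adverse Event and Other have no counterpart in Protocol 4.6 or 7.7.
- SAP IX.B: adverse events leading to study exit are tabulated apart from those leading to treatment discontinuation, so the SAP category is not just another name for stopping treatment.

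**Step 2: what Table 1c does with such a subject.** If a death by data cutoff is known, the first row counts it as an event, with no condition that the subject was still on study. If no death is known, the discontinued-study row censors at exit. The result therefore depends on whether anyone asks about vital status after exit. The Protocol requires it; the SAP does not say that it continues for these two categories.

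**Step 3: illustrative size.** Inputs from the documents: N = 24 treated (SAP II.C) and median OS 14.9 months, the figure quoted for pembrolizumab monotherapy in Protocol 1.1. Assumptions, not in the documents: exponential survival; k = 0 to 4 subjects leave alive at month 3; their hazard is then multiplied by HR = 1, 2 or 4.

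λ = ln 2 / 14.9 = 0.0465 per month.

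With exits censored, Kaplan-Meier estimates exp(−12λ) = 57.2% at 12 months, with median 14.9 months, whatever k and HR are.

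With exits followed, S(12) = exp(−12λ) − (k/24) × [exp(−9λ) − exp(−9λ·HR)], where exp(−9λ) = 0.658, and the last term is 0.433 for HR 2 and 0.187 for HR 4. The overstatement is therefore about 0.94 points per exit for HR 2, (0.658 − 0.433)/24, and 1.96 points per exit for HR 4, (0.658 − 0.187)/24.

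| Exits k | HR | 12-month OS if followed | Overstatement (points) | Median if followed (months) |
|---|---|---|---|---|
| 0, or any k with HR 1 | – | 57.2% | 0 | 14.9 |
| 1 | 2 | 56.3% | 0.9 | 14.5 |
| 1 | 4 | 55.3% | 2.0 | 14.1 |
| 2 | 2 | 55.3% | 1.9 | 14.1 |
| 2 | 4 | 53.3% | 3.9 | 13.3 |
| 4 | 2 | 53.5% | 3.8 | 13.3 |
| 4 | 4 | 49.4% | 7.8 | 11.8 |

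For scale, the approximate 95% half-width at 12 months with 24 subjects is 1.96 × √(0.572 × 0.428 / 24) = 0.198, about 20 points.

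**The case against.** The best reply is that SAP VII.B is a reporting list, not an exit rule. It sits under Disposition and ends with how percentages are calculated. On conduct, SAP II.A agrees with the Protocol that posttreatment subjects who have not met study discontinuation criteria remain on study for follow-up. Exits under these categories may then be few or none. This stands as a limit on the likely size. It does not settle the matter, because the Table 1c row acts on whatever exits are recorded. Nor does the clause that the SAP governs: it covers analysis of the data, not when a subject may leave follow-up.

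A reader might go further and infer that high-risk subjects are in fact being informatively censored and that OS is biased upward. The documents do not support that. They give no number of such exits, Other need not mean raised risk, and a death learned of after exit can still count through the first row of Table 1c.

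A reader might also size the bias from the 12% adverse-reaction discontinuation rate quoted in Protocol 1.1. That is a rate of stopping pembrolizumab, which is exactly what the Protocol distinguishes from leaving the study.

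Nor should the Protocol 4.6 list be read as strictly closed: section 8.3.2 has pregnancy documented as a reason for study discontinuation. Deleting Other, or dropping the table of adverse events leading to study exit, would therefore lose recorded information, including the display that shows whether the problem arose.

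Finally, the exits are not invisible. The SAP tabulates study-discontinuation reasons and deaths. What is missing is the link to OS censoring.

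**Conclusion.** The conflict between SAP VII.B with Table 1c and Protocol 4.5, 4.6 and 7.7 is real, and the passages should be reconciled. The bias is conditional: it needs at least one exit for an adverse event (or another risk-related reason), raised risk afterwards, and no later vital-status contact. Under the stated assumptions it ranges from nil to 7.8 points in 12-month OS, with the median overstated by up to 3.1 months (14.9 against 11.8). The upper end rests on four exits and a fourfold hazard, neither of which comes from the documents. Even that is well inside sampling error, and SAP II.C makes all analyses descriptive and exploratory. The case for change is that it is cheap and restores follow-up the Protocol already requires, not that a large distortion has been shown.

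**What to change.** Keep the disposition categories and the tables of adverse events leading to study discontinuation. Then:

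1. State in the SAP that subjects recorded as leaving for Adverse Event or Other without withdrawing consent stay in LTSFU under Protocol 7.7, and that their deaths by data cutoff are OS events.
2. Apply the Table 1c discontinued-study row only where no further vital-status contact is possible, for example after consent withdrawal. Otherwise censor at last known alive date or data cutoff, as the SAP OS text already says. Items 1 and 2 belong together: counting later deaths while censoring survivors at exit would tilt the estimate downward.
3. Split the label Discontinued from study by exit reason in the summary of OS censoring.

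The cost is SAP wording and a few phone contacts already scheduled in Protocol Table 1. Those contacts are available only while the study is open, and SAP II.F ends it 30 days after the last ongoing subject's last dose, so the clarification should come before then.
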